### **Characterization of Vaccine-Induced Antibody Profiles Weeks 0, 8, 16, 24, 32, 40, 48, 60, 76, 100, and 124**

**Purpose:** To characterize vaccine-induced antibody profiles using HER2 peptide microarrays, examining reactivity to HER2 extracellular (EC), transmembrane (TM) and intracellular (IC) domains to document evidence of epitope spreading.

To characterize immunoglobulin sub-classes of anti-HER2 antibodies.

**Specimen Processing:** No additional specimens to be drawn.

Will utilize clinical specimens drawn and processed for quantitative anti-HER2 antibody testing.

### **Cellular Responses to HER2/neu:**

#### **Weeks 0, 8, 16, 24, 32, 40, 48, 60, 76, 100, and 124Tetramer & IFN- $\gamma$ ELISPOT Assays:**

3 10mL Green Top Heparinized Tubes (30 mL total)

Send via Frederick Courier to NCI Frederick Clinical Support Laboratory for specimen processing and freezing.

**Tetramer Assay:** Will be performed by the flow cytometry unit in the NCI Frederick Clinical Support Laboratory or Vaccine Branch Flowcytometry Core.

**IFN- $\gamma$  ELISPOT Assay:** Will be performed in the Laboratory of Cell Mediated Immunity or Vaccine Branch Flowcytometry Core.

The Clinical Support Laboratory, Leidos Biomedical Research, Inc., processes and cryopreserves samples in support of IRB-approved, NCI clinical trials. The laboratory is located in a controlled access building and laboratory doors are kept locked at all times. Upon specimen receipt, each sample is assigned a unique, sequential laboratory accession ID number. All products generated by the laboratory that will be stored either in the laboratory freezers or at a central repository facility are identified by this accession ID. An electronic database is used to store information related to patient samples processed by the laboratory. Vial labels do not contain any personal identifier information. Samples are stored inventoried in locked laboratory freezers and are

routinely transferred to the NCI-Frederick repository facilities for long-term storage. These facilities are operated by ATCC, under subcontract to Leidos Biomedical Research, Inc. Access to stored clinical samples is restricted. Investigators establish sample collections under “Source Codes” and the investigator is responsible for the collections, typically the protocol Principal Investigator who has access to the collection. Blood and tissue specimens collected in the course of this research project may be banked and used in the future to investigate new scientific questions related to this study. However, this research may only be done if the risks of the new questions were covered in the consent document, the patient has provided consent for the research use of their clinical specimens, and the proposed research has undergone prospective IRB review and approval. The NIH Intramural IRB will be notified when samples are destroyed.

## **15.7 APPENDIX 7 EVALUATION OF ANTI-AD5 ANTIBODY IMMUNITY**

**An intramural scientific collaborator or scientific contractor to perform these studies to be determined.**

**Anti-Ad5 antibody ELISA assessments will be performed at**

**Weeks 0, 8, 16, 24, 32, 40, 48, 60, 76, 100, and 124**

**to determine in an exploratory manner if:**

1. AdHER2 DC vaccination is associated with a measurable increase in anti-Ad5 antibody over time.
2. Pre-existing levels of anti-Ad5 antibodies inversely correlate with vaccine immunogenicity as measured by anti-HER2 antibody levels.

We will store the samples in a -80°C freezer until batched shipped at which point they will be processed.

## **15.8 APPENDIX 8CHARACTERIZATION OF SOLUBLE HER2 AND ANTI-HER2 ANTIBODIES**

Testing and characterization of soluble HER2 and anti-HER2 antibodies will be performed by a third party Midissia or other third-party collaborator using samples stored as described in

**Appendix 6**. Midissia is a developing biopharma company that has licensed the AdHER2 DC platform in combination with a checkpoint inhibitor.

## 15.9 APPENDIX 9EXPLORATORY CORRELATIVE STUDIES

1 of 2

### Measurement of Function-Associated mRNAs in Whole Blood: Hitachi Chemical

**Function-Associated mRNAs:** One 6 mL green top sodium heparin tube  
(Week -0)

#### *For Prediction of Responses:*

- Blood will be drawn into one 6 mL green top tube.
- Add 180  $\mu$ L each of blood into one 8-well strip. Strips contain PHA, HAG, PBS, DMSO, rIL2, CEF, LPS/ZA, and HER2).
- Incubate at 37°C for 4 hours.
- Store in -80°C (+/- 10°C) freezer until ready for shipment to Hitachi Chemical
- **Note: specimen should be drawn DAY OF VACCINE before 1pm** to allow adequate time for specimen processing and four hour incubation by [name] lab staff.

*For Characterization of Responses will be assessed after “Prediction of Responses” described above confirms the list of mRNA to pursue.*

- Blood will be drawn into one 6 mL green top tube.
- Approximately 1% ( $2 \times 10^5$  cells) of final AdHER2 DC vaccine product in 0.1mL of standard suspension (taken at the same time as DC product QC test samples) and 0.2mL of heparinized whole blood will be placed into conical freezer microtubes in the following manner:
  1. **Tube 1:** 0.1mL of  $2 \times 10^5$  cells of final AdHER2 DC vaccine product **only**
  2. **Tube 2:** 0.1mL of  $2 \times 10^5$  cells of final AdHER2 DC vaccine product **plus** 0.2mL of heparinized whole blood.
  3. **Tube 3:** 0.2mL of heparinized whole blood **only**
- Incubate at 37°C for 4 hours.
- Store in -80°C (+/- 10°C) freezer until ready for shipment to Hitachi Chemical
- **Note: specimen should be drawn DAY OF VACCINE before 1pm** to allow adequate time for specimen processing and four hours incubation by [name] lab staff.

**Multiparameter Flow Cytometric Analysis of Circulating Tumor Cells (CTC) and Immune Cell Subsets: [name], DTB**

Analysis will be performed by the laboratory of [name]. CTC cells and immune cell subsets will be identified by mulitparameter flow cytometry. The order of priority for immune subset analysis is T, B, NK, NKT, Tregs, MDSC and dendritic cells.

**CTC Analysis:** One 10mL lavender top tube  
**(Weeks 0, 8, 16, 24, 32, 40, 48, 60, 76, 100, and 124 when patient schedule permits collection before 1pm.)**

**Immune Cell Subset Analysis:** One 10mL lavender top tubes  
**(Weeks 0, 8, 16, 24, 32, 40, 48, 60, 76, 100, and 124 when patient schedule permits collection before 1pm.)**

Multiparametric flow cytometry using a Miltenyi Quant flow cytometer. The order of priority for immune subset analysis is T, B, NI, NKT, Tregs, MDSC and dendritic cells.

**NKT Cell Analysis:** One 10mL lavender top tubes  
**(Weeks 0, 12 (s/p 3 doses of vaccine), 28 and 48)**

***Sample Logistics for both Function-Associated mRNAs and CTC and Immune Subsets:***

- **Notify the [name] lab via email** when the clinical sample is scheduled to be drawn:
  - [name] ([[contact]](mailto:[contact]))
  - [name] ([[contact]](mailto:[contact]))
  - [name] ([[contact]](mailto:[contact]))
- Label the clinical specimen tubes and *include the study week number*.
- **Note: specimen should be drawn before 1pm** to allow adequate time for four hours incubation for the Hitachi clinical specimens.
- **Phone the [name] lab at [contact]** when the specimen is drawn for pick up by the [name] lab.
- The laboratory of [name] where specimens will be processing and cryopreserved is in [name]

***Immune and molecular profiling through RNA sequencing:***

Briefly, patient blood samples collected at baseline and at each time point when vaccine is administered is analyzed via next generation sequencing and RNA sequencing with the aim of identifying potential biologic/immunological correlates of vaccine mediated efficacy, including but not limited to the potential upregulation of checkpoints using advanced bioinformatics tools.

**Subcontractor:** Novogene Corporation, Inc. [name] by Midissia Therapeutics, Inc.

**Specimen Processing:** 10ml of whole blood will be collected in should be in 2 Tempus RNA tubes at Weeks 0, 8, 16, 24, 30, and 48 and kept frozen at -80°C in Frederick Leidos lab until analysis. If Tempus tube sample is not available, any unused PBMNC frozen aliquots for cellular response evaluation can be used as an alternative.

RNAseq will be performed on patient blood samples to provide a comparative analysis of gene expression at baseline and following treatment. This will provide a longitudinal scan of patient response to treatment. To ensure Quality control, RNA quantity and quality are assessed using OD260 and OD260/280 ratios. RNAseq read quality is also subject to diligence. Each patient sample will have the entire transcriptome read and comparisons to baseline will be made by number of reads at each gene.

[figure not shown]
Significant changes will be determined by a threshold p-value and a list of Differentially Expressed Genes (DEG) will then be assembled. DEG gene lists will then be used as input for *post-hoc* analysis. *Differential Expression analysis* provides data on the number of genes whose expression changes over the course of treatment and is presented by Venn diagram or volcano plot. *Gene Set Enrichment Analysis* uses the lists of differentially expressed genes (DEG) and compares them to sets of curated gene sets in 4 databases.

- Gene Ontogeny (GO): a curated gene set associated with normal cell processes, such as: *regulation of cell motility*.
- Disease Ontogeny (DO): a curated gene set associated with disease processes, such as: *thrombocytosis*
- Kyoto Encyclopedia of Genes and Genomes (KEGG): a curated gene set associated with signal transduction pathways.
- Reactome: Another database of signal transduction nodes.

DEG lists from patients will be used to identify genes associated with signal transduction pathways, cellular processes and disease states to identify individual genes or groups of genes associated with a gene set of interest. Those genes whose expression patterns change predictably with clinical response will ultimately be used as a biologic/immunological correlate of vaccine mediated efficacy.

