## **10 COLLABORATIVE AGREEMENTS**

### **10.1 TECH TRANSFER AGREEMENTS**

Stored samples are being sent to Midissia for testing and characterization of soluble HER2 and anti-HER2 antibodies as a part of this protocol using a Material Transfer Agreement (MTA #42793) which was executed on 09/17/2017. There is also a CDA between Midissia and the NCI (CDA #13887-18, executed 11/10/2017). Additional tech transfers include:

- CRADA # 03048, executed 03/02/2016
- MTA #44020-28, executed 01/24/2018
- MTA #3394-13, executed 11/13/2014
- CRADA #03225, currently being negotiated

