## 11.3 OVERVIEW

In addition to reporting the observed fraction with toxicity, the 80% and 95% confidence intervals about this fraction will be reported.

At the conclusion of the study, the overall fractions with cardiac toxicity among 18, 24 or 30 patients enrolled at one dose or within the entire cohort will be determined. For illustrative purposes only, under a simplifying assumption that the 18-30 patients were enrolled in a single cohort without any intermediate evaluations, the following probabilities suggest that 2+/18, 2+/24 or 3+/18 with cardiac toxicity are more likely to be associated with 15% toxicity (arbitrarily chosen to substantially exceed 7%) than with 3% (arbitrarily chosen to be well below 7%).

In any given 18 patients assessed for toxicity, if two or more of the 18 develop toxicity:

- There is a 10% probability of this occurring if the true toxicity is 3%.
- There is a 78% probability of this occurring if the true toxicity is 15% (potentially unacceptable).

In any given 24 patients assessed for toxicity (6 at one dose level and 18 at a second level), if two or more of the 24 develop toxicity:

- There is a 16% probability of this occurring if the true toxicity is 3%.

- There is an 89% probability of this occurring if the true toxicity is 15% (potentially unacceptable).

If there are 30 patients assessed for toxicity (18 at one dose level plus 6 at one level and 6 at another level), if three or more of the 30 develop toxicity:

- There is a 6% probability of this occurring if the true toxicity is 3%.
- There is an 85% probability of this occurring if the true toxicity is 15% (potentially unacceptable).

As of 12/11/15, 0 of 20 patients enrolled to date that have received a minimum of 2 doses of AdHER2 DC vaccine have developed cardiac toxicity. Since we have observed 0 of 20 subjects with cardiac toxicity, this would have a 68% chance of occurring if the true probability of cardiac toxicity for a given patients was 2%; similarly, it would be 36% if the probability of cardiac toxicity was 5%, 12.2% if the probability of cardiac toxicity was 10% and 3.8% if the probability of cardiac toxicity was 15%. We are assuming that the probability of cardiac toxicity is no more than 10% since higher probabilities of toxicity are associated with a much lower chance of seeing 0 of 20 patients with cardiac toxicity as has been observed.

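### RNA sequencing may use a frozen PBMC aliquot in place of whole-blood RNA with no rule that baseline and follow-up samples match, so a mixed pair can show a false change

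*Combined protocol and SAP*

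**What the plan says.** The RNA sequencing subsection of Appendix 9 (Section 15.9) makes whole blood the main specimen, collected in "2 Tempus RNA tubes at Weeks 0, 8, 16, 24, 30, and 48". It then allows a substitute: "If Tempus tube sample is not available, any unused PBMNC frozen aliquots for cellular response evaluation can be used as an alternative".

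Those aliquots come from the cellular-response draw in Appendix 6 (Section 15.6), which uses "3 10mL Green Top Heparinized Tubes (30 mL total") at Weeks 0, 8, 16, 24, 32, 40, 48, 60, 76, 100 and 124. The blood is processed and frozen.

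On analysis, Appendix 9 says: "Each patient sample will have the entire transcriptome read and comparisons to baseline will be made by number of reads at each gene". A p-value threshold, whose level is not given, turns these comparisons into a list of differentially expressed genes. The changes are to be read as the patient's response to treatment over time. Genes that move predictably with clinical response are to serve as a correlate of vaccine efficacy. Section 1.1.2 includes biologic and immunologic correlates of clinical response among the secondary objectives.

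**The concern.** Whole blood and separated mononuclear cells (PBMC) are different tissues for this purpose. Whole-blood RNA includes granulocyte and red-cell transcripts; a mononuclear preparation removes most of those cells, so the mononuclear transcripts take a larger share of the reads. If the baseline is one type and the follow-up is the other, many genes will differ even if the vaccine does nothing. Normalising for total reads does not correct a change in the mix of cells.

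The substitution is allowed sample by sample, while the contrast is within patient. The stated quality checks (RNA quantity, optical-density ratios, read quality) would not reveal a difference in type. Appendix 9 also hopes to detect checkpoint upregulation. A checkpoint gene expressed mainly on mononuclear cells would seem to rise whenever a whole-blood baseline is paired with a PBMC follow-up. At stake is whether the gene lists describe the vaccine or the specimen.

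**Working it through.** The documents give no sample size, effect size, variance or error rate for the RNA sequencing, so there is no stated figure to reproduce. The check has three steps. Steps 2 and 3 use assumed values.

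**1. Is there a matching or adjustment rule?** Appendix 9 sets no condition on the substitute beyond a Tempus sample being unavailable. Section 5.1 and Section 11 give no analysis rule for RNA sequencing, and the Study Calendar (Section 3.4) has no RNA-sequencing row. No text requires matched types, excludes mixed pairs, or adds a sample-type or cell-composition term.

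**2. Shift in one mixed pair.** Assume that mononuclear cells supply a fraction f of whole-blood RNA and about all of PBMC RNA, that the gene is expressed only in mononuclear cells, and that the vaccine has no effect. The apparent change from a whole-blood baseline to a PBMC follow-up is log2(1/f):
- f = 0.2: log2(5) = +2.3
- f = 0.4: log2(2.5) = +1.3
- f = 0.6: log2(1.67) = +0.7

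The reverse pairing gives the same size with a negative sign.

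**3. Effect on a group test.** Let s0 be the share of PBMC samples at baseline, st the share at follow-up, and D the shift in log2 units. Assume substitution is independent between the two times.
- Bias in the group mean = (st − s0) × D
- Share of mixed pairs = s0(1 − st) + st(1 − s0)

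False positives were simulated with a one-sample t-test on the log2 change: true effect 0, within-patient SD 0.5, two-sided p < 0.05, 20,000 runs. Section 3.1 supplies the two group sizes: 30 patients per Part and 12 in the Part I expansion cohort. With D = 1.0:

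| s0 / st | Mixed pairs | Bias (log2) | False positives, n = 12 | False positives, n = 30 |
|---|---|---|---|---|
| 0% / 0% or 100% / 100% | 0% | 0 | 5% | 5% |
| 20% / 20% | 32% | 0 | 5% | 5% |
| 0% / 10% | 10% | +0.10 | 7% | 13% |
| 0% / 20% | 20% | +0.20 | 14% | 37% |
| 10% / 40% | 42% | +0.30 | 24% | 55% |
| 50% / 0% | 50% | −0.50 | 59% | 97% |

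For example, in the second row the mixed share is 0.2 × 0.8 + 0.2 × 0.8 = 0.32 and the bias is (0.2 − 0.2) × 1.0 = 0. With 20% substitution at one time only, the range over D = 0.5 to 1.5 is about 16% to 53% for n = 30 and 9% to 17% for n = 12.

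Matched types remove the problem. Equal substitution rates protect the group mean, but each mixed pair still carries the full shift, which matters because the contrast is described sample by sample.

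**The case against.** The strongest reply is that the defect is conditional and its size unknown. The documents do not say how often a Tempus tube is missing. A patient whose samples are all of one type has a sound contrast. This stands: a reader might infer that sample type will appear as a vaccine effect throughout the study, but the text supports that only for mixed pairs.

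A reader might also infer that patients enrolled by 2015 have only PBMC and later patients have Tempus, so that type tracks dose and Part. The dates that suggest this are in Section 10.1 (an agreement "which was executed on 09/17/2017") and Section 11.3 ("As of 12/11/15, 0 of 20 patients enrolled to date"). The documents do not support the inference. Section 10.1 ties that agreement to soluble HER2 and antibody testing, the count in Section 11.3 concerns cardiac toxicity, and nothing dates the start of Tempus collection. Even if it were true, a patient with only PBMC samples would have matched pairs.

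Nor can one say that the artefact exceeds a plausible vaccine effect, since no expected expression change is given for comparison. It would also be wrong to treat every flagged gene as an artefact. Appendix 9 carries forward only genes that track clinical response. If tubes are missing independently of response, the mismatch mainly adds noise to that association; it biases the association if missingness is related to response.

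Finally, the subsection is an outline and contains a figure that could not be read here, so an adjustment may exist elsewhere. That limits certainty, but the comparison written in the text has no safeguard.

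**Conclusion.** The concern holds for mixed pairs. Followed as written, Appendix 9 permits a whole-blood sample to be compared with a mononuclear-cell sample from the same patient, and the difference to be read as response to treatment. Group means are biased only when substitution rates differ between baseline and follow-up.

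The absence of a matching rule comes from the text. The size does not: the false-positive rates depend on the assumed shift, SD and imbalance in substitution. They show that a modest imbalance can matter and do not estimate what will happen in this trial.

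Severity is low. The work is an exploratory correlative study, and the cardiac-safety and antibody objectives do not depend on it. The correction is still worthwhile because it removes an avoidable bias from lists intended as a correlate of efficacy.

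**What to change.** Add a short paragraph to Appendix 9:

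- Each baseline-versus-follow-up contrast uses two samples of the same type.
- For a patient with a missing Tempus tube, use that patient's PBMC samples at both times where unused aliquots remain. PBMC draws are scheduled at Weeks 0, 8, 16, 24 and 48. Week 30 has no PBMC draw and no Study Calendar visit, so it has no substitute. The calendar footnote limits research samples from Week 40 onward to patients without progression.
- Exclude any remaining mixed pair from the main analysis; it may be shown as a sensitivity analysis.
- Analyse the Tempus and PBMC sets separately, or include sample type as a factor in the model.
- Stratify any between-patient association with response by sample type, and report the number of samples of each type at each week.

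The cost is one paragraph and the loss of some mixed pairs from an exploratory analysis. No new blood draw is needed. Appendix 9 keeps the Tempus samples frozen until analysis, so the rule can be set before any samples not yet sequenced are run.

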## 15.10 APPENDIX 10AD5F35HER2ECTM (ADHER2) VECTOR MANUFACTURING GMP Production Outline (1 of 2)

[figure not shown]
### Adenoviral Vector GMP Production Outline (CAGT, Baylor College of Medicine)

[figure not shown]
Ad5f35HER2ECTM (AdHER2) Detailed Vector Manufacturing  
 QC Highlighted in Orange

(2 of 2)

GMP PRODUCTION OF ADENOVIRAL VECTOR  
 MASTER VIRUS BANK Ad5f35-Her2-ECTM (VM1003)

## 15.11 APPENDIX 11 MAP OF THE Ad5F35HER2ECTM (AdHER2) VECTOR

## 15.12 APPENDIX 12 ADHER2 DENDRITIC CELL VACCINE CANCER TREATMENT HISTORY

### Brief Cancer History:

Cancer Diagnosis		
Date of Diagnosis		
Stage of Cancer		

### Surgical Procedures:

Operative Procedure	Date	Comments

### Prior Chemotherapy:

Agent/Regimen	Date/Duration	Comment/Reason for D/C

### Prior HER2-Targeted Therapies: (trastuzumab, lapatinib, pertuzumab)

Agent	Date/Duration	Comment/Reason for D/C
HISTORY OF HER2 THERAPY RELATED CARDIAC DYSFUNCTION (If yes document name of agent and describe toxicity and intervention)	YES	NO

**PATIENT IS NOT ELIGIBLE FOR THIS STUDY IF POSITIVE FOR HER2-RELATED CARDIAC TOXICITY**

### Prior Radiation Therapy

Therapy Type	Date/Duration	Comment

### Pathology: HER2/neu expression

HER2 Detection Method	Negative	Equivocal	Positive
Vysis FISH Ratio (Measures HER2 oncogene)	Ratio < 1.8	Ratio 1.8 – < 2.2	Ratio > 2.2
IHC (Measures HER2 protein)	0	1+ - 2+	3+

### Part I and Part II Inclusion

*Part I: Adults ≥ 18 with recurrent or progressive, metastatic solid tumors characterized by some HER2/neu expression that have failed standard therapies with known benefit but for whom trastuzumab is not clinically indicated.*

*Part II: Breast cancer patients with 3+ HER2/neu expression by IHC or a positive or an equivocal or positive FISH result with prior exposure to trastuzumab, lapatinib or pertuzumab.*

Part I or Part II	HER2 Detection Method	Expression	Date of Collection	Received from NIH or Outside Lab
	Vysis FISH Ratio			
	IHC			

Additional Comments:

Person Completing This Form: \_\_\_\_\_

## **15.13 APPENDIX 13 PATIENT RECRUITING MATERIALS**

**In accordance with standard IRB regulations requiring approval of patient recruitment materials,** The following script is for an informational video that will be posted to the NCI YouTube Network sponsored by the NCI Office of Communications at: [www.youtube.com/ncigov](http://www.youtube.com/ncigov). The informational video will feature [name], the former Principal Investigator of the AdHER2 DC vaccine study and will be approximately 2-4 minutes in duration. The video link will be embedded in all standard patient recruitment materials sent out by the NCI CCR Office of Patient Outreach and Recruitment as well as the NIH Clinical Center Office of Communications, Patient Recruitment and Public Liaison. This informational video is a novel patient recruitment tool that is being piloted with this study and will be assessed for its impact on rates of study accrual.

